3.3.4 Withdrawal of patients from treatment or assessments

Patients may potentially be withdrawn from trial treatment or from the trial as a whole ("withdrawal of consent") with very different implications, please see [sections 3.3.4.1](#) and [3.3.4.2](#) below.

Every effort should be made to keep the randomised patients in the trial. Measures to control the withdrawal rate include careful patient selection, appropriate explanation of the trial requirements and procedures prior to randomization, as well as the explanation of the consequences of withdrawal.

Patients who fail to complete all treatment and PASAPQ as required in the protocol, will not be considered complete. The decision to withdraw from trial treatment or from the whole trial as well as the reason must be documented in the patient files and Case Report Form (CRF).

3.3.4.1 Discontinuation of trial treatment

An individual patient will discontinue trial treatment if:

- The patient wants to discontinue trial treatment, without the need to justify the decision.
- The patient has repeatedly shown to be non-compliant with important trial procedures and, in the opinion of both, the investigator and sponsor representative, is not willing or able to adhere to the trial requirements in the future.

Proprietary confidential information © 2020 Boehringer Ingelheim International GmbH or one or more of its affiliated companies

- The patient needs to take concomitant medication that interferes with the investigational medicinal product or other trial treatment.
- The patient can no longer receive trial treatment for medical reasons (such as surgery, adverse events, other diseases, or pregnancy).

In case of a temporary reason, trial treatment should be restarted if medically justified, please see [Section 4.1.4.](#)

Even if the trial treatment is discontinued, the patient remains in the trial and, given his/her agreement, will undergo the procedures for early treatment discontinuation and follow up as outlined in the [Flow chart](#) and section.

3.3.4.2 Withdrawal of consent to trial participation

Patients may withdraw their consent to trial participation at any time without the need to justify the decision.

If a patient wants to withdraw consent, the investigator should be involved in the discussion with the patient and explain the difference between trial treatment discontinuation and withdrawal of consent to trial participation, as well as explain the options for continued follow up after trial treatment discontinuation, please see [Section 3.3.4.1](#) above.

3.3.4.3 Discontinuation of the trial by the sponsor

Boehringer Ingelheim reserves the right to discontinue the trial overall or at a particular trial site at any time for the following reasons:

1. Failure to meet expected enrolment goals overall or at a particular trial site.
2. Emergence of any efficacy/safety information invalidating the earlier positive benefit-risk-assessment that could significantly affect the continuation of the trial.
3. Violation of Good Clinical Practice (GCP), the trial protocol, or the contract impairing the appropriate conduct of the trial.

The investigator/the trial site will be reimbursed for reasonable expenses incurred in case of trial termination (except in case of the third reason).

4. TREATMENTS

4.1 INVESTIGATIONAL TREATMENTS

4.1.1 Identity of the Investigational Medicinal Products (IMPs)

The test product Tiotropium Respimat® (Spiriva® Respimat®), and the comparator product Tiotropium Handihaler® (Spiriva®) will be supplied by Boehringer Ingelheim Pharma GmbH & Co. KG, Germany. The composition of the drugs is described as follow:

Table 4.1.1:1 Test product: Tiotropium Respimat® (Spiriva® Respimat®)

Substance:	Tiotropium
Pharmaceutical formulation:	inhalation solution
Source:	Boehringer Ingelheim Pharma GmbH & Co. KG, Germany
Unit strength:	2.5µg per puff, 60 puffs with 1 Respimat® Inhaler
Posology:	5 µg once daily, given as 2.5µg per puff, two puffs
Method and route of administration:	Oral Inhalation via Respimat®

Table 4.1.1:2 Comparator products: Tiotropium Handihaler® (Spiriva®)

Substance:	Tiotropium
Pharmaceutical formulation:	Inhalation Powder
Source:	Boehringer Ingelheim Pharma GmbH & Co. KG, Germany
Unit strength:	30 capsules with 1 Handihaler® device
Posology:	18µg once daily
Method and route of administration:	Oral Inhalation via Handihaler®

Proprietary confidential information © 2020 Boehringer Ingelheim International GmbH or one or more of its affiliated companies

Tiotropium Respimat® and Tiotropium Handihaler® both have the same active ingredient in the medicine: tiotropium bromide.

Tiotropium Respimat® delivers a very slow-moving mist that is designed to help the patient inhale the medicine easier. The amount of medicine the patient takes in does not depend on how fast they are able to inhale. Patients receive one dose per day, which lasts for 24 hours.

The medicine in Tiotropium Handihaler® comes in a dry powder contained in a capsule that is put into a special inhaler. The patient takes the medicine by breathing in two inhalations through the Handihaler®. The medicine lasts for 24 hours, so patients take one dose (two inhalations) of Tiotropium Handihaler® per day in the morning. Patients use a new capsule for each dose.

4.1.2 Selection of doses in the trial and dose modifications

Tiotropium Respimat® and Tiotropium Handihaler® have been available on the market, so dose selection please follow the local package inserts, that is, randomized patients will receive tiotropium 5 µg inhalation solution from the Respimat® inhaler or tiotropium inhalation capsules 18 µg delivered by the HandiHaler®.

4.1.3 Method of assigning patients to treatment groups

Technical and statistical features of the process of treatment sequence allocation are provided in [Section 7](#).

Each patient will get a patient number when informed consent is signed at Visit 1 and a randomization number at Visit 2, which will be recorded in the electronic case report form (eCRF).

Since the medication dispensed to the patient is one device of Respimat® or Handihaler® each time, only the device type will be recorded in the eCRF and there will be no medication number.

After assessment of all in- and exclusion criteria, each eligible patient will be randomised to the open-label phase of the trial (Visit 2) during which one group of patients will receive 5µg tiotropium (2 puffs of 2.5µg) administered once daily by Respimat® (T1), the other group will receive 18µg tiotropium once daily by Handihaler® (T2) for 4 weeks.

Randomisation of patients to treatment sequence is based on randomization envelope at visit 2. After the first 4-week treatment, these two treatment groups of patients will switch to the Tiotropium Respimat® and Tiotropium Handihaler® vice versa. The appropriate randomization number and correspondent device type will be assigned by randomization envelope at Visit 2. Note that there is no medication number exists during the study and medication device type should be recorded in eCRF.

4.1.4 Drug assignment and administration of doses for each patient

At Visit 1, all patients should be trained on the use of rescue medication Salbutamol Sulphate Aerosol (pMDI).

Proprietary confidential information © 2020 Boehringer Ingelheim International GmbH or one or more of its affiliated companies

At Visit 2 and Visit 3, patients will be assigned to one of the two treatment groups. At each of these visits, patients will be trained on how to use the Tiotropium Respimat® or Handihaler® properly.

4.1.4.1 Instructing the patient

Detailed written instructions and training for the use of the Respimat®, Handihaler® and Salbutamol Sulphate Aerosol will be given to the patient at Visit 2 and 3 (see [Section 10.1](#), [10.2](#) and [10.3](#)).

The Respimat® inhalers and cartridges will be dispensed to patients unassembled and packaged in one box (each box containing one Tiotropium Respimat® inhaler and one Tiotropium Respimat® cartridge), and patients will be instructed on how to prepare the inhaler for use, including inserting the cartridge into the inhaler and priming the unit, and on using the Tiotropium Respimat® inhaler.

Note: Patients who are randomized to Tiotropium Respimat® must follow the instructions for this inhaler in Section 10.1. These patients must be instructed to take two puffs of Tiotropium Respimat® one time a day.

Patients who are randomized to Tiotropium Handihaler® must follow the instructions for this product according to Section 10.2. These patients must take one capsule of tiotropium bromide once daily with the HandiHaler® device at the same time of day.

Table 4.1.4.1: 1 Dosage and treatment schedule

Treatment	Visit Number	Tiotropium Respimat®	
		μg/daily	
1	Visit 2 - Visit 3 (Week 0-4)	5μg (2 puffs of 2.5μg)	-
	Visit 3 - Visit 4 (Week 4-8)	-	18μg (one capsule)
2	Visit 2 - Visit 3 (Week 0-4)	-	18μg (one capsule)
	Visit 3 - Visit 4 (Week 4-8)	5μg (2 puffs of 2.5μg)	-

The Tiotropium Respimat® contains 60 puffs per cartridge and 2.5μg tiotropium per puff, with drug concentration of 0.2262 mg/ml (calculated as tiotropium) after preparing the inhaler for first use. There is enough medicine for 30 days when it is used as two puffs of Tiotropium Respimat® one time a day.

Each Tiotropium Handihaler® contains 30 capsules with the HandiHaler® device. Each capsule contains 18μg (as tiotropium, equivalent to 22.5μg tiotropium bromide monohydrate), enough for 30 days if used as one capsule once daily with the HandiHaler® device.

Two treatment groups of patients will be assigned to therapy with either Tiotropium

Proprietary confidential information © 2020 Boehringer Ingelheim International GmbH or one or more of its affiliated companies

Respimat® or Tiotropium HandiHaler® for 4 weeks respectively before completing the PASAPQ at a single visit to the study site.

4.1.4.2 Trial medication administration at home

Patients will be instructed to refer to the detailed written inhaler directions provided at either Visit 2 or Visit 3, or to phone the site if they have questions.

The patient will record whether he/she took the daily doses (number of puffs or capsule) of the medication in a patient diary. If a patient misses a dose, he/she should take the next dose at the next scheduled time and make a note of the missed dose in his/ her patient diary.

4.1.4.3 Trial medication return

All used and unused trial medication, used device will be returned to the clinic at the next treatment visit.

Any inhaler that is reported to have malfunctioned by the patient or study staff should be returned to BI for further investigation. Please see the ISF for specific instructions regarding the procedure to return such devices.

Note: Tiotropium HandiHaler® capsules are to be used only with the HandiHaler® device. Tiotropium Respimat® cartridges are to be used only with the Respimat® inhaler.

4.1.5 Blinding and procedures for unblinding

Not applicable.

4.1.6 Packaging, labelling, and re-supply

The investigational products will be provided by BI. They will be labelled in accordance with the principles of Good Manufacturing Practice (GMP). Re-supply to the sites will be managed via site staff and CRA, which will also monitor expiry dates of supplies available at the sites.

For details of the description of the label, refer to the ISF.

4.1.7 Storage conditions

Trial medication must be stored under the recommended storage conditions indicated on the drug information leaflets.

- Tiotropium Respimat®: Do not freeze. Store in a safe place out of the reach of children!
- Tiotropium Handihaler®: Do not store above 25°C. Do not freeze. Store in a safe place out of the reach of children!
- Salbutamol Sulphate Aerosol: Store under 30°C. Keep away from light and avoid freezing and direct sunlight.

A temperature log must be maintained by the site to make certain that the drug supplies are stored at the correct temperature. If the storage conditions are found to be outside the

Proprietary confidential information © 2020 Boehringer Ingelheim International GmbH or one or more of its affiliated companies

specified range, the Clinical Trial Manager (CTM) for the study should be contacted immediately.

Trial medication must be stored securely at the study sites, out of reach of children and be protected from freezing, e.g. in a locked cupboard or at a pharmacy. It may only be dispensed to trial patients fulfilling the inclusion and exclusion criteria by authorized study personnel as documented in the ISF. Receipt, usage, and return of the study medication must also be documented on the respective forms in the ISF.

4.1.8 Drug accountability

The investigator or designee will receive the investigational drugs delivered by the sponsor when the following requirements are fulfilled:

- Approval of the clinical trial protocol by the IRB / ethics committee ,
- Availability of a signed and dated clinical trial contract between the sponsor and the investigational site,
- Availability of the curriculum vitae of the Principal Investigator,
- Availability of a signed and dated clinical trial protocol,
- Availability of the proof of a medical license for the Principal Investigator

IMPs are not allowed to be used outside the context of this protocol. They must not be forwarded to other investigators or clinics. Patients should be instructed to return unused IMPs.

The investigator or designee must maintain records of the product's delivery to the trial site, the inventory at the site, the use by each patient, and the return to the sponsor or warehouse / drug distribution centre or alternative disposal of unused products. If applicable, the sponsor or warehouse / drug distribution centre will maintain records of the disposal.

These records will include dates, quantities, batch / serial numbers, expiry ('use- by') dates, medication device type and trial patients. The investigator or designee will maintain records that document adequately that the patients were provided the doses specified by the Clinical Trial Protocol (CTP) and reconcile all IMPs received from the sponsor. At the time of return to the sponsor, the investigator or designee must verify that all unused or partially used drug supplies have been returned by the clinical trial patient and that no remaining supplies are in the investigator's possession.

4.2 OTHER TREATMENTS, EMERGENCY PROCEDURES, RESTRICTIONS

4.2.1 Other treatments and emergency procedures

• Rescue medication(s)

Salbutamol Sulphate Aerosol (pMDI) will be provided as rescue medication. Administration of rescue medication can occur at any time during the study. The number of puffs used for rescue will be recorded by the patient in the Patient Diary. In the case of potentially life-

Proprietary confidential information © 2020 Boehringer Ingelheim International GmbH or one or more of its affiliated companies

threatening COPD exacerbations, any and all therapies and interventions deemed medically necessary by the treating physician could be prescribed.

The following medications are allowed to control acute exacerbations as medically necessary during the treatment period.

1. As needed (PRN) Salbutamol Sulphate Aerosol (pMDI) (provided by [REDACTED] and to be recorded on the Patient Diary).
2. Temporary of nebulised short-acting β agonist (SABA) and/or short-acting muscarinic antagonist (SAMA) can be allowed during exacerbation.
3. Temporary increases in the dose of theophylline preparations of up to 7 days each are allowed during the study. Temporary increases in the dose or addition of, oral steroids of up to 7 days each are allowed during the study.
4. The use of antibiotics is not restricted and may be used as medically necessary for exacerbations and other infections.

4.2.2 Restrictions

4.2.2.1 Restrictions regarding concomitant treatment

Table 4.2.2.1:1 Restrictions for concomitant treatment

Drug class	Screening period	Treatment period
Oral corticosteroids ¹ (≤ 10 mg prednisone per day)	Permitted	Permitted
Inhaled corticosteroids ¹	Permitted	Permitted
Theophylline ¹	Permitted	Permitted
Mucolytics ¹	Permitted	Permitted
Antihistamines, Antileukotrienes, Cromolyn ¹	Permitted	Permitted
Inhaled long-acting-beta-adrenergics ¹	Permitted	Permitted
Oral beta-adrenergics ¹	Permitted	Permitted
Inhaled short-acting-beta-adrenergics	PRN as supplied for study only - recorded in patient Diary	PRN as supplied for study only - recorded in patient Diary

Proprietary confidential information © 2020 Boehringer Ingelheim International GmbH or one or more of its affiliated companies

Inhaled short-acting-anticholinergics	Only for exacerbation treatment.	Only for exacerbation treatment.
Inhaled long-acting-anticholinergics	Not permitted	Trial medication

1. If stabilized for 6 weeks before screening (visit 1)

The following inhalation devices or medications are **not allowed** during the screening period or the treatment period.

- Inhalation devices other than the investigational devices which have not been stably used for 6 weeks prior to the screening period.
- Use of systemic corticosteroid medication at unstable doses (i.e., less than six weeks on stable dose) or at doses in excess of the equivalent of 10 milligrams (mg) prednisolone per day.
- Long-acting anticholinergic drugs other than the investigational drugs during the randomization treatment period.

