### 6.2 IMPORTANT PROTOCOL DEVIATIONS

All subjects with important deviations from the protocol will be listed (Appendix 16.2 of the CTR). The IN/EX numbers refer to the definition given in the CTP and CRF.

Subjects with potentially important protocol deviations (iPDs) will be identified based on Table 6.2: 1 and documented. The table defines the different categories of important PDs. The final column describes which PDs will be used to exclude subjects from the different subject analysis sets.

The list of PDs in Table 6.2: 1 is considered a 'working' list, which is expected to be updated throughout the trial and finalized prior to the Database Lock (DBL). In any case, all important PDs will be tracked during the study at Medical Quality Review Meetings (MQRMs) or Blinded Reported Plan Meeting (BRPM) to verify the quality of the inclusion and the conduct of the study.

Table 6.2: 1 Important protocol deviations

Category / Code		Description	Requirements	Excluded from
A		Entrance criteria not met		
	A1	Inclusion criteria not met	Inclusion criteria 5 not met as specified in the protocol.	None
	A2	Exclusion criteria not met	Exclusion criteria 1, 2, 3 not met as specified in the protocol	None
B		Informed consent		
	B1	Informed consent not available/not done	Informed consent date missing	All
	B2	Informed consent too late	Informed consent date was after Visit 2 date	None
C		Trial medication		
	C1	Incorrect trial medication taken during study	Incorrect trial medication taken during study Incorrect rescue medication taken during study	None
	C2	Randomization not followed	Not following randomized treatment sequence or randomized treatment devices	None
D		Concomitant medication		
		Prohibited medication use during study	According to CTP section 4.2.2.1 Restrictions regarding concomitant treatment	None
E		Missing critical data		
	E1	Primary endpoint related data missing	Patients missed PASAPQ both in Visit 3 and Visit 4	FAS

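### Oral steroid courses and nebulised bronchodilators that Protocol 4.2.1 allows for exacerbations conflict with Protocol 4.2.2.1, and SAP deviation category D cites only 4.2.2.1

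*Protocol*

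**What the plan says.** **Protocol 4.2.1** introduces its list this way: "The following medications are allowed to control acute exacerbations as medically necessary during the treatment period". On steroids it says: "Temporary increases in the dose or addition of, oral steroids of up to 7 days each are allowed during the study". On nebulised treatment it says that "nebulised short-acting β agonist (SABA) and/or short-acting muscarinic antagonist (SAMA) can be allowed during exacerbation". The list also covers study salbutamol as needed, theophylline increases of up to 7 days, and antibiotics without restriction.

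**Protocol 1.4** also lets exacerbations be treated with oral steroids and antibiotics as medically needed, but states no 7-day limit. It adds that trial medication may be continued through the treatment period or after the episode.

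**Protocol 4.2.2.1** has a table and a list.
- The list of what is not allowed in the screening or treatment period includes "Use of systemic corticosteroid medication at unstable doses (i.e., less than six weeks on stable dose", together with doses above 10 mg prednisolone equivalent per day.
- The same list bars inhalation devices, other than the investigational ones, that were not in stable use for 6 weeks before screening.
- The table row for inhaled short-acting beta-agonists reads "PRN as supplied for study only - recorded in patient Diary".
- The row for inhaled short-acting anticholinergics does carry an exception for treating exacerbations.
- Footnote 1 makes oral steroids (up to 10 mg prednisone per day), theophylline and several other classes conditional on 6 weeks' stability before Visit 1.

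**SAP 6.2, Table 6.2:1**, defines prohibited medication in category D as "According to CTP section 4.2.2.1 Restrictions regarding concomitant treatment". It does not mention 4.2.1. The exclusion column for category D reads None. Patients with important deviations are to be listed in an appendix of the trial report. The table is described as a working list, to be finalised before database lock.

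**The concern.** Two sections of one protocol give different answers for the same patient in the same week. An investigator who turns to 4.2.1 finds a short steroid course or a nebuliser allowed. One who turns to 4.2.2.1 finds the steroid course on the list of what is not allowed and the beta-agonist limited to the study inhaler. Nothing says which section takes precedence.

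The SAP then settles the conflict in one direction for reporting, because category D looks only to the restrictive section. The important-deviation listing would mix patients treated as the protocol permits with patients who really departed from it, for example by taking another long-acting anticholinergic. A reader of the report could not separate the two from the category alone. What is at stake is consistent conduct across about 7 sites and a deviation listing that means what it says.

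**Working it through.** The plan states no figure on this point. The check sets the passages side by side, with one comparison of durations.

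**Steroids.**
- Longest single addition or increase under 4.2.1: 7 days.
- Stability required by 4.2.2.1: 6 weeks × 7 = 42 days.
- 7 < 42, so no course given within the 4.2.1 limit can reach the required stability. Each is an unstable dose under 4.2.2.1 at any milligram dose. The separate 10 mg ceiling is a second way to be caught, but the result does not depend on it.
- Neither the bar nor the table row has an exacerbation exception or a reference to 4.2.1. This is a direct contradiction.

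**Each item that 4.2.1 allows, against 4.2.2.1:**

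| Item in 4.2.1 | Position in 4.2.2.1 | Result |
|---|---|---|
| Oral steroid addition or increase, up to 7 days | Barred as unstable; no exception | Contradiction |
| Nebulised short-acting beta-agonist | Study supply only (a metered-dose inhaler); device bar | Contradiction |
| Nebulised short-acting anticholinergic | Drug allowed for exacerbations; device bar | Conflict through the device bar only |
| Theophylline increase, up to 7 days | Not on the barred list; footnote concerns stability before screening | Unclear at most |
| Antibiotics | Not listed | No conflict |
| Study salbutamol as needed | Allowed | No conflict |

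The device bar reaches nebulisers because Protocol 1.1 counts them among inhaler devices. A patient already using a nebuliser stably for 6 weeks before screening would escape that bar, but nebulised beta-agonist would still fall outside the study supply.

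**Carry-over to the SAP.** Category D tests against 4.2.2.1 alone, so the first two rows are flagged outright and the third is flagged through the device bar. Category C1 also mentions incorrect rescue medication. It does not say what counts as incorrect, so it neither adds to nor removes the problem.

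**Effect on the analysis.** Category D removes nobody from the treated set or the full analysis set. The patients, the scores and the mixed model are the same whether or not the flag is set.

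**The case against.** The strongest reply is that 4.2.1 is the specific rule and 4.2.2.1 the general one. Section 4.2.1 speaks expressly of exacerbations in the treatment period, and 1.4 supports it. The steroid bar repeats exclusion criterion 15, which suggests that a rule about background therapy was carried over from the entry criteria. The SAP table is a working list reviewed before database lock, so wrongly flagged patients can be removed.

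Much of this is fair, and the intent may well be as described. But no text gives 4.2.1 precedence. The 4.2.2.1 table does write an exacerbation exception for short-acting anticholinergics, so its silence on steroids and beta-agonists cannot safely be read as an oversight. A correction to the SAP list alone would also leave the sites' instructions unreconciled.

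A reader might infer three stronger things, which the documents do not support.
- *That 4.2.2.1 bars exacerbation care in general.* It does not. Antibiotics, study salbutamol and short-acting anticholinergics as a drug class are not barred. A patient whose theophylline was stable before screening still meets the footnote after a later increase.
- *That patients would be lost from the primary comparison.* Section 3.3.4.1 stops treatment for medication that interferes with trial treatment, and nothing says an exacerbation course does. Section 1.4 lets trial medication continue, and 6.2.2 asks patients who stop early to complete the Visit 4 procedures, including the questionnaire. For potentially life-threatening exacerbations, 4.2.1 allows any therapy deemed necessary.
- *That flagged patients use up the margin of 71 − 60 = 11.* Protocol 7.7 sets that margin aside for patients without evaluable data. A category D flag does not make data unevaluable.

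**Conclusion.** The text is wrong as written for systemic corticosteroids and for nebulised short-acting bronchodilators. For steroids, every addition or increase within the 4.2.1 limit breaches 4.2.2.1. For nebulised beta-agonist, the supply rule and the device bar both conflict with 4.2.1. For nebulised anticholinergic, only the device bar does. Taken literally, category D lists these patients as important deviations although 4.2.1 permits their treatment.

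The number of patients affected cannot be derived, because the documents give no exacerbation rate. The consequence is contradictory site instructions and a misleading deviation listing. The flag does not alter the analysis sets, the primary estimate or power.

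The conclusion rests on reading 4.2.2.1 literally, with no unstated precedence for 4.2.1, and, for the device bar, on counting a nebuliser as an inhalation device. It takes no position on which clinical rule is right.

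**What to change.** 1. The sponsor's clinical team should reconcile Protocol 1.4, 4.2.1 and 4.2.2.1 (both table and list) for systemic corticosteroids and nebulised treatment. Each class should have one stated position for background use and one for exacerbations, with a cross-reference between 4.2.1 and 4.2.2.1. The absence of the 7-day limit in 1.4 should be settled at the same time, and the theophylline footnote can be clarified in the same edit.
2. SAP Table 6.2:1, category D, should then cite both 4.2.1 and 4.2.2.1 as reconciled, so that use the protocol permits is not flagged. This should be done before database lock, while the table is still a working list.

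The cost is a wording change in a few protocol paragraphs and one cell of the SAP table. No analysis, sample size or data collection changes. Until the protocol is reconciled, the deviation review meetings named in SAP 6.2 should check any category D steroid or nebuliser case against 4.2.1 before calling it important.
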